5.8.2. Analysis of Adverse Events of Special Interest

Treatment emergent adverse events of special interest for adjudicated arthropathy and sympathetic nervous system dysfunction will be presented by SOC and PT. The summaries will be sorted by decreasing incidence of PT within each SOC in the combined fasinumab group.

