5.8. Analysis of Safety Data

The analysis of safety and tolerability will be performed on the SAF, as defined in [Section 3.3](#). The safety analysis will be based on the reported AEs and other safety information (clinical

laboratory evaluations, vital signs, physical exam and 12-lead ECG). Thresholds for Potential Clinically Significant Values (PCSV) in laboratory variables, vital signs and ECG are defined in [Appendix 10.2](#).

The summary of safety results will be presented for each treatment group.

Period of observation: The observation period will be divided into three segments: pre-treatment, on-treatment, and follow-up period.

- The pre-treatment period is defined as the time from signing the ICF to before the first dose of study drug.
- The on-treatment period is defined as the day from first dose of study drug to 4 weeks after the last dose of SC study drug or 8 weeks after the last dose of IV study drug, whichever is later.
- The Post/Treatment follow-up period is defined as from the end of the on-treatment period+1 day to the end of study visit (week 36).

Unless otherwise noted, summaries of safety variables will use data from the on-treatment period. Listings of safety variables will include data from all periods and values occurring during the pre-treatment and follow-up period will be flagged in the listings.

Day 1 is the first day of investigational product, Day –1 is the day before, and there is no Day 0.

The time interval to detect any on-treatment event or abnormality is the on-treatment period. Data collected outside this interval will be excluded from the estimation of descriptive statistics and identification of abnormalities for laboratory evaluations, ECGs and vital signs. All post-baseline data during the interval will be using in the PCSV analysis including scheduled and unscheduled assessments.

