5.8.1. Adverse Events

The verbatim text, the PT, and the primary SOC will be listed in patient listings. Summaries that include frequencies and proportions of patients reporting AEs will include the PTs and the SOCs.

Pre-treatment AEs are defined as AEs that developed or worsened during the pre-treatment period.

Treatment-emergent AEs (TEAEs) are defined as AEs that developed or worsened during the on-treatment period.

Post-treatment AEs are defined as AEs that developed or worsened more than 28 days after the last SC dose of investigational product or 56 days after the last IV dose of investigational product.

The focus of adverse event reporting in the clinical study report will be on TEAEs. Post-treatment AEs and AEs during the combined study periods will also be summarized.

For details on handling missing data and partial dates, see [Section 6](#).

Summaries of all TEAEs in each treatment group will include:

- Overview of TEAEs, summarizing number of events, summarizing number and percentage of patients with any
 - Total number of TEAEs
 - Total number of Serious TEAEs
 - Patients with any TEAEs
 - Patients with Serious TEAEs
 - Patients with TEAE leading to permanent treatment discontinuation
 - Patients with TEAE leading to withdrawal from study
 - Patients with TEAE leading to death
 - Patients with any AESI's
- TEAEs by SOC and PT
- TEAEs by SOC, PT, and severity
- Treatment-related TEAEs by SOC, PT, and severity
- TEAEs Resulting in Permanent Study Drug Discontinuation by SOC and PT
- AESI by SOC and PT
- Post-Treatment TEAEs by SOC and PT
- Post-Treatment TEAEs by SOC, PT, and severity
- All On-Treatment and Post-Treatment AEs by SOC and PT
- All On-Treatment and Post-Treatment AEs by SOC, PT, and severity
- Serious TEAEs by SOC and PT
- Non-serious TEAEs by SOC and PT
- Post-treatment Serious AEs by SOC and PT
- All Serious AEs by SOC and PT
- Listing of Patients with Serious TEAEs
- Listing of Patients with AESIs
- Listing of deaths
- Listing of AEs leading to death

Counts will be provided by treatment group for each PT within each SOC. Percentages will be calculated using the number of patients from the SAF in each treatment group.

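### No planned table is assured to give a by-arm, whole-study count of committee-confirmed arthropathy, the type of event that led to the clinical hold

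*SAP*

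**What the plan says.** The main passages on safety periods are these.

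- SAP 5.8 sets the default: "Unless otherwise noted, summaries of safety variables will use data from the on-treatment period". It also states: "The summary of safety results will be presented for each treatment group". Listings cover all periods.
- SAP 5.8 ends the on-treatment period at "4 weeks after the last dose of SC study drug or 8 weeks after the last dose of IV study drug, whichever is later". Follow-up starts the next day and runs to the week-36 visit. Protocol 9.5.3.1 has the same on-treatment rule and equates its end with week 16.
- SAP 5.8.2 covers AESIs: "Treatment emergent adverse events of special interest for adjudicated arthropathy and sympathetic nervous system dysfunction will be presented by SOC and PT".
- SAP 5.8.1 also plans an AESI table by system organ class (SOC) and preferred term (PT), with no period of its own. It stands in a list introduced as TEAE summaries, but that list also holds post-treatment tables.
- SAP 5.8.3 plans by-arm summaries of joint replacements and of replacements in positively adjudicated joints. SAP 5.8.8 plans a summary of arthropathy adjudications. Neither names a period.
- SAP 5.8.4 to 5.8.6 do name periods for potentially clinically significant values (PCSVs): on-treatment, post-treatment and overall.
- SAP 4.5.2 selects AESIs by a tick box on the adverse-event page. Protocol 3.3.2 gives the determination of arthropathy to an adjudication committee.
- SAP section 1 explains that an adjudicated arthropathy preceded the partial clinical hold, that dosing stopped early, and that patients are to be followed to week 36, partly to keep monitoring safety.

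**The concern.** Patients stay in the study to week 36 so that safety, joint safety above all, can be observed after dosing stopped. The tables dedicated to that question are either limited to treatment-emergent events or silent on period under an on-treatment default. For laboratory values, vital signs and ECGs the authors wrote out all three periods; for the event behind the hold they did not.

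There is also a question of what is counted. The AESI tables count ticked boxes, not committee verdicts. The adjudicated part of 5.8.3 counts replacements, so a confirmed case without surgery does not enter it. The adjudication summary in 5.8.8 states no unit. At stake is whether the report gives, for each arm and the whole study, the number of patients with confirmed arthropathy.

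**Working it through.** **Inputs.** All arms receive SC and IV study drug: SC on days 1, 29, 57 and 85, IV on days 1 and 57 (protocol 3.1 and Table 1). The dosing window is ±7 days (protocol 5.1). The week-36 visit is on day 253 ±7 (protocol Table 2).

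**The plan's own figure.** On-treatment end = max(last SC day + 28, last IV day + 56). For full dosing this is max(85 + 28, 57 + 56) = day 113, which is week 16, as protocol 9.5.3.1 says.

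**By last dosing visit, on schedule.** Post-baseline days are days 2 to 253, that is 252.

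| Last dosing visit | SC + 28 | IV + 56 | On-treatment ends | Days left to 253 | Share of 252 |
|---|---|---|---|---|---|
| Day 1 | 29 | 57 | 57 | 196 | 78% |
| Week 4 | 57 | 57 | 57 | 196 | 78% |
| Week 8 | 85 | 113 | 113 | 140 | 56% |
| Week 12 | 113 | 113 | 113 | 140 | 56% |

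**With the dosing window.** For a last dosing visit at week 8 or 12 the end moves between days 106 and 120. For week 4, SC + 28 is day 50 to 64 and IV + 56 is day 57, so the end is day 57 to 64.

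**Routine MRI of knees and hips with K-L grade 3 or more.** The week-36 MRI falls on days 246 to 260, and the on-treatment period ends by day 120 at the latest, so it is always outside. The week-16 MRI (days 106 to 120) is outside for patients last dosed on day 1 or at week 4. For those last dosed at week 8 or 12 it can fall on either side.

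**Tracing one case.** Take an arthropathy with onset at the week-36 MRI, confirmed by the committee.
- 5.8.2: not counted, because it is not treatment-emergent.
- 5.8.8: not counted under the 5.8 default.
- 5.8.3: counted only if the joint is replaced, and only if the table is read as whole-study.
- 5.8.1, AESI by SOC and PT: undetermined, because no period is stated.
- 5.8.1, post-treatment and combined-period tables: counted by arm if reported as an adverse event, but under its preferred term. Arthropathy is an umbrella for three conditions (protocol 1.1), and these tables do not show the committee's verdict.
- AESI listing: shown if the box was ticked, but a listing is not a by-arm count.

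**Secondary points.**

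(a) SAP 5.8.1 defines post-treatment events as those that "developed or worsened more than 28 days after the last SC dose of investigational product or 56 days after the last IV dose", without saying that the later limit applies. Read literally, post-treatment starts at min(last SC + 28, last IV + 56) + 1, which is day 30, 58, 86 or 114 for the four rows. The overlap with the on-treatment period is 28 days for day 1 (days 30 to 57), 0 for week 4, 28 for week 8 (days 86 to 113) and 0 for week 12. The table label Post-Treatment TEAEs also conflicts with the definition of a TEAE in the same section.

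(b) For laboratory values, ECGs and vital signs, 5.8 says: "Data collected outside this interval will be excluded from the estimation of descriptive statistics and identification of abnormalities". It gives no explicit limit to on-treatment analyses, and sits awkwardly beside the by-visit summaries and the post-treatment and overall PCSV summaries in 5.8.4 to 5.8.6.

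(c) Protocol 3.1 lists three AESIs, including joint replacement. Protocol 7.2.3 and SAP 4.5.2 list two.

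**The case against.** The strongest reply is that nothing is lost. Section 5.8.1 plans by-arm post-treatment tables, combined-period tables and all-serious-event tables, and the AESI listing covers every period. That stands: a reader might infer that follow-up arthropathies would vanish from the report, and the documents do not support it. But neither the tables nor the listing is a by-arm count of confirmed cases.

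Second, 5.8.3 need not be on-treatment. The default governs safety variables, SAP 4.5 does not list joint replacement among them, and protocol Table 3 follows surgery for 20 weeks. This reading is possible, so the on-treatment reading of 5.8.3 is the more natural one but not certain. The argument is weaker for 5.8.8, whose title refers to safety variables.

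Third, a reader might infer that 5.8 flatly contradicts 5.8.4 to 5.8.6. It does not have to. The exclusion sentence directly follows one about detecting on-treatment abnormalities and can be read as confined to on-treatment analyses. The next sentence, "All post-baseline data during the interval will be using in the PCSV analysis including scheduled and unscheduled assessments", does not say that only those data are used. A clarifying clause is enough.

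Fourth, the missing qualifier in 5.8.1 is most likely shorthand for the rule in 5.8, and Post-Treatment TEAEs is a labelling slip. The AESI-list mismatch changes little analysis, because 5.8.3 summarises joint replacements anyway. All three are editorial.

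**Conclusion.** The main point holds. A team that follows the SAP exactly can produce AESI and adjudication tables that omit arthropathy with onset in follow-up, and no table is assured to count committee-confirmed cases by arm over the whole study. Presentation by arm is assured; the whole-study period and the committee-confirmed unit of count are not.

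The time outside the on-treatment period is 56% or 78% of post-baseline days. This assumes on-schedule dosing and follow-up to day 253. A reader might take these as the share of events missed, but the documents give no event timing and do not say how many patients had each last dosing visit. The 28-day overlap likewise assumes on-schedule dosing and a literal reading, and arises only when the last dose was on day 1 or at week 8. The main gap is worth fixing; items (a) to (c) are clarifications.

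**What to change.** - In SAP 5.8.2, 5.8.3 and 5.8.8, specify by-arm summaries for the on-treatment period, the post-treatment period and the study overall, using the period terms of 5.8.4 to 5.8.6. Cover patients with committee-confirmed arthropathy (from the adjudication result, not the tick box), sympathetic nervous system dysfunction and joint replacement.
- In 5.8.1, state the period of the AESI table by SOC and PT. Define post-treatment events as those with onset after the end of the on-treatment period, and relabel Post-Treatment TEAEs as Post-treatment AEs.
- In 5.8, state that the exclusion of laboratory, ECG and vital-sign data applies only to on-treatment summaries.
- Reconcile the AESI lists in protocol 3.1, protocol 7.2.3 and SAP 4.5.2.

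The TEAE window in protocol 9.5.3.1 is unchanged. The cost is SAP wording, the list reconciliation and a few extra tables from data already collected.

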5.8.3. Total Joint Replacements (TJR)

Total and partial joint replacements of any joints will be summarized by treatment group. Number of replacements in joints that were positively adjudicated will be summarized by treatment group. TJRs will also be summarized by KL score of the affected joint.

5.8.4. Clinical Laboratory Measurements

A treatment-emergent Potential Clinically Significant abnormal value (PCSV) is a laboratory value that was normal or abnormal but not meeting PCSV criteria at Screening and Baseline but became abnormal and met PCSV criteria after treatment with study drug. PCSV summary will be constructed for on-treatment period, post-treatment period and overall during the study.

Baseline clinical laboratory analytes and change from Baseline in clinical laboratory analytes to each scheduled assessment time will be summarized with descriptive statistics. Summary statistics will include using the number of patients (n), mean, standard deviation, median, Q1, Q3, minimum, and maximum. Scatter plot of change scores from baseline of LBPI vs. Alkaline phosphatase will be plotted by treatment group and visit. Mean change from baseline in Alkaline phosphatase values along with standard error bars will be plotted over time by treatment group.

5.8.5. Analysis of Vital Signs

Vital signs (pulse, sitting blood pressures, orthostatic blood pressure/heart rate, and temperature) will be summarized by baseline and change from baseline to each scheduled assessment time with descriptive statistics. The graphs of mean (or median) value of some vital sign parameter vs. visit will also be plotted.

PCSV summary including orthostatic hypotension will be constructed for on-treatment period, post-treatment period and overall during the study.

5.8.6. Analysis of 12-Lead ECG

ECG parameters (P-R interval, QT interval, QTc interval, QRS interval, Ventricular rate and Heart rate) will be summarized by baseline and change from baseline to each scheduled and collected assessment time. PCSV summary of ECG parameters will be provided for on-treatment period, post-treatment period and overall during the study.

ECG status (i.e. normal, abnormal) will be reported. Newly occurring ECG findings will be summarized.

5.8.7. Physical Exams

The percentage of patients with new-onset abnormal physical examinations will be summarized using frequency and percentage by body system by visit..

5.8.8. Analysis Other Safety Variables

Summaries and listings will be provided for the Survey of Autonomic Symptoms and Joint Pain Questionnaire. Arthropathy adjudications based on the imaging data will also be summarized.

5.9. Analysis of Pharmacokinetic and Antibody Data

5.9.1. Analysis of Pharmacokinetic Data

Summaries of concentrations of functional fasinumab will be presented by nominal time point and dose. Plots of individual concentration will be presented by actual day (linear and log scales). Plots of mean or median concentration of functional fasinumab will be presented by nominal day and visit (linear and log scales).

5.9.2. Analysis of Anti-drug Antibody Data

The ADA variables described in [Section 4.6](#) will be summarized using descriptive statistics by dose/cohort group in the ADA analysis set. Prevalence of pre-existing immunogenicity, treatment-emergent and treatment-boosted ADA will be assessed as absolute occurrence (N) and percent of patients (%), grouped by study cohorts. Plots of drug concentrations will be examined and the influence of treatment-emergent or treatment-boosted ADA assay response on individual PK profiles will be evaluated.

Listings of ADA positivity and titers presented by patient, time point, and dose cohort/group will also be provided.

Impact of ADA on Safety and Efficacy

Correlation analysis of safety versus treatment-emergent ADA positivity status may be performed on the SAF. Assessment will focus on the following safety events:

- Hypersensitivity (SMQ : Hypersensitivity [Narrow])
- Anaphylaxis (SMQ: Anaphylaxis[Narrow])

Number (%) of patients with the above mentioned safety events may be summarized by ADA status (positive or negative), during the TEAE period.

In addition, correlation analysis of key efficacy endpoints versus treatment-emergent ADA status in patients who discontinued due to lack of efficacy may be summarized.

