9.5.5. Descriptive Analysis of Anti-Drug Antibody Data

Summaries of anti-fasinumab antibody data will be provided. Safety and efficacy will be evaluated relative to the results from the ADA assay.

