The U.S. Food and Drug Administration (FDA) placed the study on partial clinical hold before enrollment was completed and dosing was prematurely terminated before all randomized patients had completed treatment. The study was enrolling patients with chronic low back pain, some of whom had advanced osteoarthritis, to doses that exceeded those being pursued in the concurrent or planned osteoarthritis studies which limits dosing to 6 mg SC Q8W. Since an event of adjudicated arthropathy was observed in the CLBP study in a patient with advanced OA using a dose higher than that being evaluated in the ongoing OA study, the FDA requested that the study be placed on hold until the protocol could be amended to either remove patients with OA or reduce the doses. A decision was made not to amend the protocol to enable dosing to be resumed. At the time of the clinical hold, 563 patients had been randomized into the study. Patients will be encouraged to remain in the study and be followed for all study visits until completion of the week 36 visit to continue to monitor safety and to allow complete data collection.

The planned analyses take this change into account.

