3.5. The Anti-Drug Antibody Analysis Set

The anti-drug (fasinumab) antibody (ADA) analysis will include all randomized and treated patients who have at least 1 post-dose ADA result after the first dose of study treatment.

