4.6. Anti-Drug Antibody (ADA) Variables

Serum samples collected at baseline, week 16 (end of treatment) and week 36 (end of study) or ET (early termination) will be analyzed for anti-drug antibody (ADA) analysis. ADA variables include status (positive or negative) and titer as follows:

- Total number of patients whose response in the ADA assay is negative at all times
- Total number of patients whose response in the ADA assay is positive at any time point analyzed
- Pre-existing immunoreactivity - defined either as a positive ADA assay response at baseline with all post-dose ADA assay results negative, **OR** a positive assay response at baseline with all post-dose ADA assay responses less than 9-fold over baseline titer levels
- Treatment-emergent - defined as any post-treatment positive ADA assay response when the baseline is ADA negative or missing
- Treatment-boostered – defined as any post-dose positive ADA assay response that is at least 9-fold over the baseline titer level when baseline is positive in the ADA assay.
- Titer
 - Titer values
 - Titer category
 - Low (titer <1,000)
 - Moderate ($1,000 \leq \text{titer} \leq 10,000$)

- High (titer >10,000)

Neutralizing activities of ADA will be assessed for samples that are positive in the ADA assay.

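### SAP 5.9.2 narrows the protocol's ADA-versus-efficacy evaluation to an optional look at patients who stopped for lack of efficacy, a subset that weakens the contrast of interest

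*SAP*

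**What the plan says.** Protocol 9.5.5 states: "Safety and efficacy will be evaluated relative to the results from the ADA assay". It names no subset and does not make the evaluation optional.

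SAP 5.9.2 has one sentence on ADA and efficacy: "correlation analysis of key efficacy endpoints versus treatment-emergent ADA status in patients who discontinued due to lack of efficacy may be summarized". The SAP's efficacy methods (5.7) contain no analysis by ADA status, and the subgroups listed in 5.7.1 do not include it.

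The other two ADA relationships in SAP 5.9.2 are not restricted in this way. For safety, "Correlation analysis of safety versus treatment-emergent ADA positivity status may be performed on the SAF". For drug concentration, "the influence of treatment-emergent or treatment-boosted ADA assay response on individual PK profiles will be evaluated".

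A wider population is already defined. Under SAP 3.5 the ADA analysis "will include all randomized and treated patients who have at least 1 post-dose ADA result after the first dose of study treatment". SAP 4.6 places the samples at baseline, week 16, and week 36 or early termination.

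SAP 1.1.5, the section for modifications from the protocol's statistical section, says only which protocol amendment the SAP is based on.

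**The concern.** The question behind an ADA-efficacy analysis is whether patients who form antibodies do worse on the same fasinumab regimen than patients who do not. The planned subset contains only patients whose pain response was poor enough for them to stop. If antibodies reduce efficacy, they act partly by moving patients into this subset, and that movement cannot be seen by looking only inside it. What remains is a comparison among patients already alike in doing badly.

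The SAP also makes the analysis optional. The report could therefore contain no ADA-efficacy result, or one that selection has pulled towards no difference, although the protocol promised the evaluation. The restricted sentence also counts treatment-emergent status only. It omits the treatment-boosted category, which SAP 4.6 defines and the PK evaluation includes.

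**Working it through.** The documents give no sample size, rate or power for this analysis, so there is no figure to reproduce. The point rests on the text; the numbers illustrate its size.

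**1. Text side by side.**

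| Item | Population | Commitment |
|---|---|---|
| Protocol 9.5.5, ADA and efficacy | no restriction | will |
| SAP 5.9.2, ADA and efficacy | lack-of-efficacy discontinuers | may |
| SAP 5.9.2, ADA and safety | safety analysis set | may |
| SAP 5.9.2, ADA and PK | not restricted to discontinuers | will |

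Only the efficacy row is selected on outcome.

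**2. Inputs for the attenuation illustration.** The reference study quoted in SAP 2.2 gives LS mean changes (SE) of -2.18 (0.14), n = 295, and -1.25 (0.16), n = 230.
- Difference: 2.18 - 1.25 = 0.93.
- SDs: 0.14 × √295 = 2.40 and 0.16 × √230 = 2.43; pooled, 2.41.
- Assumed, not in the documents: ADA-positive patients lose the whole 0.93 points; ADA prevalence is 5–20%; stopping for lack of efficacy becomes more likely as the pain change worsens.

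**3. Fixed cut-off.** Suppose patients stop when their change exceeds a threshold t. The mean among stoppers is μ + σ·φ(z)/[1 − Φ(z)], with z = (t − μ)/σ.
- t = 0, ADA-positive (μ = -1.25): z = 0.518, ratio 1.154, mean -1.25 + 2.414 × 1.154 = 1.54.
- t = 0, ADA-negative (μ = -2.18): z = 0.903, ratio 1.448, mean -2.18 + 2.414 × 1.448 = 1.32.
- Difference among stoppers: 0.22. With t = 1 it is 2.30 − 2.13 = 0.17.

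**4. Graded stopping.** The probability of stopping is taken as logistic in the pain change with slope 1 per point (simulation of 4 million patients per setting).

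| Quantity | Result |
|---|---|
| Difference, all treated | about 0.93 |
| Difference, stoppers only | 0.48 to 0.54 |
| Stopping rate, ADA-positive | 4.5% to 15% |
| Stopping rate, ADA-negative | 2.4% to 9% |

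About half of the true difference remains among stoppers. The contrast in stopping rates is lost from the analysis, since everyone in it has stopped.

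**5. Likely numbers.** SAP section 1 reports: "At the time of the clinical hold, 563 patients had been randomized into the study". An even 1:1:1:1 split gives 563 × 3/4 = 422 on fasinumab. Assume 2–10% stop for lack of efficacy and 5–20% are ADA-positive, independently:
- Subset: 422 × 0.02 = 8 to 422 × 0.10 = 42 patients.
- ADA-positive in the subset: 8.4 × 0.05 = 0.4 to 42 × 0.20 = 8.
- ADA-positive among all fasinumab patients: 422 × 0.05 = 21 to 422 × 0.20 = 84, or about 7 to 28 per arm.

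The figure of 422 is an upper bound for the ADA analysis set, which requires treatment and a post-dose ADA result. The hold may also lower the number stopping for lack of efficacy, since "dosing was prematurely terminated before all randomized patients had completed treatment"; the SAP does not say how many patients this affected.

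**6. What the wider set would deliver.** At 10% prevalence one arm has about 14 ADA-positive and 127 ADA-negative patients. The standard error of the difference is 2.41 × √(1/14 + 1/127) = 0.68, so a 95% interval extends about ±1.3 points. The wider set removes the selection but would still be imprecise by arm.

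**The case against.** The strongest reply is that a reader might infer that an antibody effect would be invisible, with ADA-positive and ADA-negative failures looking alike. The documents do not support that. The efficacy endpoints are graded scores, not success or failure, and the illustration itself leaves a difference of 0.17 to 0.54 inside the subset.

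Enrichment could also be inferred from other planned output. Suppose 5% of ADA-negative and 20% of ADA-positive patients stop, with 10% prevalence. Then 42 × 0.20 ≈ 8 and 380 × 0.05 = 19 stop, so about 31% of stoppers are ADA-positive against 10% overall. SAP 5.9.2 commits to ADA prevalence by cohort and by-patient ADA listings, and SAP 5.5 to reasons for discontinuation by treatment. A careful reader could put these together. That stands, but it would be an unplanned reconstruction rather than the evaluation promised in the protocol.

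A reader might also infer that a stated objective is left unmet, because immunogenicity is named in the safety objectives. That objective is the incidence of antibody formation, which SAP 4.6 and 5.9.2 cover. Neither document lists the effect of ADA on efficacy as an objective.

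Nor can one conclude that placebo and fasinumab failures will be pooled. The sentence is silent on arms, while the section's other ADA summaries are by dose or cohort.

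Finally, the wider comparison has its own weakness. ADA status arises after randomization and is first sampled post-dose at week 16 or early termination, so it is not a baseline subgroup, and patients who stay longer have more chances to test positive. This is a reason to label the replacement descriptive and to avoid tabulating week 2 to 12 pain by later ADA status. It does not justify selecting on the outcome.

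**Conclusion.** The concern holds in limited form. The SAP replaces an unrestricted protocol commitment with an optional analysis in an outcome-selected subset and does not declare the change. Within that subset any ADA difference is attenuated: to roughly half under graded stopping, and to about a fifth to a quarter under a sharp cut-off. It probably rests on a handful of ADA-positive patients at most. The analysis itself cannot compare response or lack-of-efficacy discontinuation rates by ADA status. It could hint at an effect but could not estimate one or exclude one.

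The textual mismatch and the direction of the attenuation do not depend on the assumed rates, provided that stopping is related to worse pain. The sizes do: the ADA prevalence, the stopping rate, the even split and the complete loss of effect are all assumptions. No primary or secondary result changes. This is a cheap improvement.

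**What to change.** Replace the sentence in SAP 5.9.2 with:

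*Change from baseline in average daily LBPI NRS, RMDQ and PGA at week 16, and the proportion discontinuing for lack of efficacy, will be summarised descriptively by ADA status (treatment-emergent or treatment-boosted versus neither) within each fasinumab group in the ADA analysis set.*

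Add that ADA status is determined after randomization and sampled only at baseline, week 16, and week 36 or early termination, so the comparison is descriptive and not causal. If the sponsor prefers to keep the restriction, SAP 1.1.5 should declare and justify it as a departure from protocol 9.5.5.

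The cost is SAP wording and one or two descriptive tables from data already scheduled for collection. The downside is that few ADA-positive patients are expected per arm, so the tables will be imprecise and should be presented as such.
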